Our primary hypothesis is that the operative treatment group will have lower VAS pain scores compared to the non-operative treatment group both during their hospital stay and in the short-term outpatient follow-up.

Based on the results of a pilot study, we expect pain scores in the non-operative group to have a mean of 5.7 and a standard deviation of 2.3. Assuming a 20% reduction in pain scores, 130 patients (65 per arm) are required to have an 80% chance of detecting, as significant at the 5% level, a decrease in the primary outcome measure from 5.7 in the control group to 4.56 in the experimental group. This is our primary outcome and the study will be powered for this variable.

Primary data analysis will involve direct comparison of the change in value of the reported pain scores at the time points listed below. We will be powered to detect a 20% reduction in pain. Secondary analysis will compare the value of narcotics administered at the distinct time periods. Tertiary analysis will be comparing the time (in days) to mobilization with physical therapy. The previous retrospective pilot study incorporated a propensity factor, generated from well documented sources of pain. As this is a prospectively randomized trial, we do not anticipate needing to accommodate for matching.

RANDOMIZATION

Eligible patients will be randomized in equal proportions to one of the two treatment groups: 1) operative treatment of the lateral compression type fracture, 2) non-operative treatment of the lateral compression type fracture. Allocation will be concealed using a centralized 24-hour computerized randomization system, www.randomize.net, that will allow Internet based allocation. The treatment allocation will be stratified on the following prognostic factors to ensure balance between the intervention groups: 1) patient intubation status at time of enrollment, 2) patient prescription pain medication usage during the month prior to injury.

DATA MANAGEMENT

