APPENDIX B: DATA COLLECTION SCHEDULE

Assessment	Screen / Enroll	Pre-Rand. Base	Post-Rand. Base	96-hour	2 week	6 week	3 month	1 year
Pelvic x-rays	X							
Informed Consent	X							
HIPAA	X							
Stratification Levels (AF03)								
Intubation Status (at time of consent)		X						
Prescription Pain Medication Usage (during month prior to pelvic injury)		X						
Patient Intake (CRF01)								
Demographics (age, gender, race/ethnicity, education)			X					
Smoking History			X					
Previous Injuries			X					
Pre-injury Pain Medication Usage			X					
Pre-injury Work Status (WPAI:SHP)			X					
Pre-Injury Health Status (VR-12)			X					
Pre-Injury Pelvic Function (Majeed Pelvic)			X					
Index Hospitalization - Clinical Intake (CRF02)								
Length of Stay & Discharge Disposition			X					

Assessment	Screen / Enroll	Pre-Rand. Base	Post-Rand. Base	96-hour	2 week	6 week	3 month	1 year
ICU Length of Stay			X					
Date/Time & Mechanism of Injury			X					
Height & Weight			X					
Medical History			X					
Time to Mobilization (Bed to Chair)			X					
Narcotic Use			X					
OR Trip(s) Identification			X					
Classification of All Injuries			X					
Study Injury Characteristics			X					
Study Treatment Characteristics			X					
Patient Follow-Up (CRF03 & CRF04)								
Brief Pain Inventory (BPI)				X	X	X	X	X
Re-hospitalizations or Surgeries					X	X	X	X
Physical Therapy Tracking					X	X	X	X
Post-Injury Pain Medication Usage					X	X	X	X
Post-Injury Work Status (WPAI: SHP)					X	X	X	X
Post-Injury Health Status (VR-12)					X	X	X	X
Post-Injury Pelvic Function (Majeed Pelvic)					X	X	X	X
Clinical Follow-Up (CRF05)								
Ambulation & Weight Bearing Status					X	X	X	X
Pain Medication Usage					X	X	X	X
Fracture Healing Status					X	X	X	X
Complications (type, severity, treatment)					X	X	X	X

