**Pelvis RCT: Impact of Surgery on Pain in Lateral Compression Type Pelvic Fractures**

**NCT: 02625766**

**December 28, 2020**

### Statistical Analysis

[figure not shown]
The primary analyses were based on the intent-to-treat principle. The primary analysis for pain and secondary analysis for functional outcome estimated the difference in the average treatment effect based on a longitudinal assessment within the initial 12-weeks after the fracture. This approach uses each patient's multiple outcome assessments to compare the average pain and function experienced over the 12-week period between the treatment groups. For these analyses, we used a Bayesian hierarchical model that applied a prior probability of no treatment difference based on the conflicting evidence in the prior literature [3-6]. This is akin to an initial assumption that there is "no difference" in pain or functional outcome between the treatment groups. In addition to estimating the average treatment effect, we calculated the posterior probability (meaning conditioning the prior distribution on the data at hand) of treatment benefit with operative treatment under various minimally clinical important difference (MCID) thresholds. The models included a dummy variable for each patient as a random intercept, an autoregressive correlation structure, and adjusted for whether the treatment was randomly assigned, the patient's pre-injury narcotic use, and a time-varying covariate that measured narcotic use at each time point. Multivariable linear regression was used to analyze the treatment effect on hospital length of stay and time to mobilization. Outcome data were missing in 16% of the sample at 2-weeks, and 14% of the sample at 6-weeks and 12-weeks, and was therefore imputed using multiple imputation for the final models [16]. To assess possible effect measure modification based on the initial degree of displacement, we stratified the sample to create two subgroups, patients with  $\geq 5$ mm of displacement and patients with  $< 5$ mm of displacement. We then calculated the average effect of operative treatment on pain in each of the subgroups. In addition, we compared the average treatment effect of operative fixation on pain with posterior-only fixation compared to operative fixation with anterior and posterior fixation. Additional sensitivity analyses recalculated the pain and function outcomes to separately compare the treatment effects between patients enrolled in the randomized cohort and the observational cohort. The analyses were performed using R Version 3.6.1 (Vienna, Austria) with the packages *lme4*, *rstan*, *brms*, and *mice*.

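### Randomisation is stratified by intubation status, but the SAP's pain and function models omit it without a reason; in the randomised patients this makes intervals somewhat too wide, by an amount the documents do not give.

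*Protocol*

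**What the plan says.** The protocol's Randomization section allocates patients equally to operative or non-operative treatment and says: "The treatment allocation will be stratified on the following prognostic factors to ensure balance between the intervention groups". The factors follow: "1) patient intubation status at time of enrollment, 2) patient prescription pain medication usage during the month prior to injury". Appendix B places both on the stratification form (AF03), in the column for data collected before randomisation.

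The SAP's Statistical Analysis section describes a Bayesian hierarchical model for pain and function over the first 12 weeks, fitted to randomised and observational patients together. It has a random intercept per patient and autoregressive correlation, and it is "adjusted for whether the treatment was randomly assigned, the patient's pre-injury narcotic use, and a time-varying covariate that measured narcotic use at each time point". Intubation does not appear anywhere in the SAP as a covariate, subgroup or sensitivity analysis.

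For the two in-hospital outcomes the SAP says only: "Multivariable linear regression was used to analyze the treatment effect on hospital length of stay and time to mobilization". It does not list the covariates of that regression.

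**The concern.** Stratifying on a prognostic factor balances it between the arms, so its contribution drops out of the true sampling variability of the treatment difference. A model without the factor still counts that contribution as unexplained variation. In the SAP's model it would go into the variance of the patient-level intercept, because intubation status and treatment both vary between patients. The reported interval is then wider than it should be.

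No other term fills the gap. Pre-injury narcotic use corresponds to the other stratum. Narcotic use at each time point is measured after allocation and cannot stand in for a baseline factor.

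Pooling adds a second issue. Stratification balances intubation only among randomised patients. Observational patients were not allocated by it, so a difference in intubation between their operative and non-operative groups would be left uncontrolled. The protocol expects some intubated patients, since its Informed Consent section provides for consent by a representative in that case.

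**Working it through.** **Inputs from the protocol (Data Analysis).** Control mean 5.7, SD 2.3, target mean 4.56 (difference 1.14), 65 per arm, 80% power, 5% level.

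**Inputs assumed.** The share intubated, *q*, and the pain difference between intubated and other patients, *m*, are not in the documents. I use three pairs across a range: 10% and 1 point, 20% and 1.5 points, 30% and 2 points.

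**Step 1: reproduce the plan's figure.** Per arm, n = 2(1.960 + 0.842)² × 2.3² / 1.14² = 63.9, so 64 per arm or 128 in total, against the stated 130. At 65 per arm the normal approximation gives 80.7% power and the exact t calculation 80.1%. The sample size reproduces with a two-sided test and is not in question.

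**Step 2: variance carried by the stratum.** R² = q(1 − q)m² / 5.29.

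**Step 3: consequences at 65 per arm.** The unadjusted model reports SE = 2.3 × √(2/65) = 0.403. The true SE under stratified allocation is 0.403 × √(1 − R²). The overstatement is 1/√(1 − R²) − 1, and its equivalent in patients is 130 × [1/(1 − R²) − 1].

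| Assumed *q*, *m* | R² | True SE | SE overstated | Equivalent patients | Power, omitted | Power, included | Type I error, omitted |
|---|---|---|---|---|---|---|---|
| any *q*, 0 | 0 | 0.403 | 0 | 0 | 80.7% | 80.7% | 5.0% |
| 10%, 1 | 0.017 | 0.400 | 0.9% | about 2 | 80.9% | 81.3% | 4.8% |
| 20%, 1.5 | 0.068 | 0.389 | 3.6% | about 9 | 81.5% | 83.3% | 4.2% |
| 30%, 2 | 0.159 | 0.370 | 9.0% | about 25 | 82.7% | 86.9% | 3.3% |

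**Step 4: check by simulation.** I used 6,000 replicates of 130 patients, with blocks of four within strata (block size assumed) and a linear model at one time point.

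- At 30% and 2 points, the model without the stratum reports SE 0.403 against an actual 0.371, with type I error 3.4% and power 81.3%. With the stratum, the figures are SE 0.369, 4.8% and 85.7%.
- At 10% and 1 point, the SEs are 0.402 and 0.399 and the powers 80.1% and 80.5%, which is no practical difference.

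**Step 5: scale against the SAP's own output.** The last SAP table gives a mean difference of 0.9 (95% CrI 0.1 to 1.8) for displacement under 5 mm. The implied posterior SD is 1.7 / 3.92 = 0.434, which returns the tabulated 41% for a benefit above 1.0. As an outer illustration, I shrink this SD by the largest case, to 0.434 × 0.917 = 0.398, as if every patient had been randomised. The probability of a benefit above 0.5 moves from 82% to 84%, above 1.0 from 41% to 40%, and above 1.5 from 8% to 7%.

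**The case against.** The strongest reply is that the effect may be negligible. Both inputs that set its size are assumed, and at the low end of the range nothing changes that a reader would notice. That stands: one can be confident of the omission, but not of a material consequence.

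It is also fair that the calculation is not the SAP's analysis. It uses one time point, randomised patients only and a frequentist linear model. The SAP pools two cohorts over 12 weeks with multiple imputation. The direction carries over to the randomised part; the type I error and power figures do not transfer to the pooled model.

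Several stronger readings are tempting, but the documents do not support them.

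- **That the randomised comparison is biased.** It is not. Allocation was stratified, and the error makes a test of no difference conservative.
- **That the pooled effect is materially confounded.** One can assume a 15-point intubation imbalance and a 2-point pain difference and obtain 0.15 × 2 = 0.30 points of bias. Neither input is in the documents, and the figure applies only to the observational contrast, so pooling shrinks it. The SAP also analyses the randomised patients separately and reports a benefit there that is at least comparable. That check does not remove an imbalance from the pooled estimate, but it limits how far one could be driving the conclusion. The SAP's term for whether treatment was randomised does not control intubation within the observational cohort.
- **That intubation is missing from the length-of-stay and mobilisation models.** Their covariates are not listed, so this cannot be established.
- **That the second stratum is also ignored.** Pre-injury narcotic use is not worded as the stratum is, but the protocol's secondary endpoints draw narcotic use partly from a pain-medication questionnaire, so the overlap is substantial.
- **That the covariate is already on file for everyone.** AF03 is a pre-randomisation form, and the documents do not say that it was completed for patients who were never randomised.

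**Conclusion.** The point holds as a modest one. One of two factors that the protocol itself calls prognostic and randomises by is left out of the pain and function models without explanation. In the randomised patients this costs precision: about 1% to 9% on the standard error over the assumed range, nothing if intubation does not predict pain, and at most about 4 percentage points of power in the single-time-point calculation. Those figures rest on SD 2.3 and on assumed values for the share intubated and its pain difference. In the pooled estimate there is also a possible uncontrolled imbalance among observational patients. Its size and direction cannot be derived from the documents.

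**What to change.** Add intubation status at enrolment as a fixed effect in the pain and function models, and enter the medication factor in the categories used for randomisation. Put both in the imputation model too, since 14% to 16% of outcomes were imputed.

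Do this at least in the randomised-cohort analysis, where AF03 should supply both values. Extend it to the pooled models where intubation is recorded for observational patients or can be taken from the medical record. List the covariates of the length-of-stay and mobilisation regressions and use the same factors there.

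If intubation is to stay out, for example because very few patients were intubated, state the number and the reason and show a sensitivity analysis that includes it.

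The SAP describes analyses already run, so the cost is a re-run with one or two more covariates, plus possible record review for observational patients if AF03 was not completed for them.

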APPENDIX B: DATA COLLECTION SCHEDULE

Assessment	Screen / Enroll	Pre-Rand. Base	Post-Rand. Base	96-hour	2 week	6 week	3 month	1 year
Pelvic x-rays	X							
Informed Consent	X							
HIPAA	X							
Stratification Levels (AF03)								
Intubation Status (at time of consent)		X						
Prescription Pain Medication Usage (during month prior to pelvic injury)		X						
Patient Intake (CRF01)								
Demographics (age, gender, race/ethnicity, education)			X					
Smoking History			X					
Previous Injuries			X					
Pre-injury Pain Medication Usage			X					
Pre-injury Work Status (WPAI:SHP)			X					
Pre-Injury Health Status (VR-12)			X					
Pre-Injury Pelvic Function (Majeed Pelvic)			X					
Index Hospitalization - Clinical Intake (CRF02)								
Length of Stay & Discharge Disposition			X					

Assessment	Screen / Enroll	Pre-Rand. Base	Post-Rand. Base	96-hour	2 week	6 week	3 month	1 year
ICU Length of Stay			X					
Date/Time & Mechanism of Injury			X					
Height & Weight			X					
Medical History			X					
Time to Mobilization (Bed to Chair)			X					
Narcotic Use			X					
OR Trip(s) Identification			X					
Classification of All Injuries			X					
Study Injury Characteristics			X					
Study Treatment Characteristics			X					
Patient Follow-Up (CRF03 & CRF04)								
Brief Pain Inventory (BPI)				X	X	X	X	X
Re-hospitalizations or Surgeries					X	X	X	X
Physical Therapy Tracking					X	X	X	X
Post-Injury Pain Medication Usage					X	X	X	X
Post-Injury Work Status (WPAI: SHP)					X	X	X	X
Post-Injury Health Status (VR-12)					X	X	X	X
Post-Injury Pelvic Function (Majeed Pelvic)					X	X	X	X
Clinical Follow-Up (CRF05)								
Ambulation & Weight Bearing Status					X	X	X	X
Pain Medication Usage					X	X	X	X
Fracture Healing Status					X	X	X	X
Complications (type, severity, treatment)					X	X	X	X

APPENDIX C: CONSENT TEMPLATES

See attachment.

APPENDIX D: AFs and CRFs

See attachment.

**Pelvis RCT: Impact of Surgery on Pain in Lateral Compression Type Pelvic Fractures**

**NCT: 02625766**

**December 28, 2020**

### Statistical Analysis

[figure not shown]
The primary analyses were based on the intent-to-treat principle. The primary analysis for pain and secondary analysis for functional outcome estimated the difference in the average treatment effect based on a longitudinal assessment within the initial 12-weeks after the fracture. This approach uses each patient's multiple outcome assessments to compare the average pain and function experienced over the 12-week period between the treatment groups. For these analyses, we used a Bayesian hierarchical model that applied a prior probability of no treatment difference based on the conflicting evidence in the prior literature [3-6]. This is akin to an initial assumption that there is "no difference" in pain or functional outcome between the treatment groups. In addition to estimating the average treatment effect, we calculated the posterior probability (meaning conditioning the prior distribution on the data at hand) of treatment benefit with operative treatment under various minimally clinical important difference (MCID) thresholds. The models included a dummy variable for each patient as a random intercept, an autoregressive correlation structure, and adjusted for whether the treatment was randomly assigned, the patient's pre-injury narcotic use, and a time-varying covariate that measured narcotic use at each time point. Multivariable linear regression was used to analyze the treatment effect on hospital length of stay and time to mobilization. Outcome data were missing in 16% of the sample at 2-weeks, and 14% of the sample at 6-weeks and 12-weeks, and was therefore imputed using multiple imputation for the final models [16]. To assess possible effect measure modification based on the initial degree of displacement, we stratified the sample to create two subgroups, patients with  $\geq 5$ mm of displacement and patients with  $< 5$ mm of displacement. We then calculated the average effect of operative treatment on pain in each of the subgroups. In addition, we compared the average treatment effect of operative fixation on pain with posterior-only fixation compared to operative fixation with anterior and posterior fixation. Additional sensitivity analyses recalculated the pain and function outcomes to separately compare the treatment effects between patients enrolled in the randomized cohort and the observational cohort. The analyses were performed using R Version 3.6.1 (Vienna, Austria) with the packages *lme4*, *rstan*, *brms*, and *mice*.

We took two critical steps to understand the potential for biased treatment estimates from pooling the results from the randomized and non-randomized participants. First, we performed sensitivity analyses to separately examine the results for the randomized and non-randomized cohorts. These analyses suggested similar (or even larger) estimated treatment benefits from surgery within the RCT data. Second, we included willingness to be randomized as a potentially confounding variable in our final analysis models, despite there being no evidence that it affected treatment.

[figure not shown]
The ability to assess the probability of different magnitudes of treatment benefit is a unique characteristic of Bayesian data analysis, and is not possible with traditional non-Bayesian statistical hypothesis testing. Despite this inherent difference in statistical principles, it should be noted that the average treatment benefits reported from our Bayesian analysis are nearly identical to the results obtained using traditional multilevel linear regression models (results not reported).

Additional results from the described analyses, that were not included in the main article, are provided below.

[figure not shown]
**Posterior probability of reduced pain.** Posterior probability of reduced pain with operative treatment within 12 weeks of injury.

[figure not shown]
**Mean pain stratified between randomized and nonrandomized patients.** The mean Brief Pain Inventory scores and 95% credible intervals within the initial 12-weeks of injury for minimally displaced complete lateral compression pelvis fracture patients. The patients are stratified based on their study type (randomized trial versus observation) and treatment type (operative versus nonoperative treatment). The pain scores are adjusted for the study type, prior narcotic use, and narcotic use at each time point.

**Posterior probability of improved function.** Posterior probability of improved function, measured with the Majeed score, with operative treatment within 12 weeks of injury.

**Mean function stratified between randomized and nonrandomized patients.** The mean Majeed scores and 95% credible intervals within the initial 12-weeks of injury for minimally displaced complete lateral compression pelvis fracture patients. The patients are stratified based on their study type (randomized trial versus observation) and treatment type (operative versus nonoperative treatment).

**Posterior probability of reduced pain, stratified by initial posterior pelvic ring fracture displacement:** The posterior probability of surgical fixation achieving a clinically significant reduction in mean BPI pain scores stratified by fracture displacement (<5mm versus  $\geq$ 5mm). Several possible clinically significant pain reduction thresholds are presented.

	Displacement $\geq$ 5mm	Displacement < 5mm	Difference in Probability
Mean Difference in Pain	2.2 (95% CrI: 0.9 - 3.5)	0.9 (95% CrI: 0.1 - 1.8)	
> 0	> 99%	98%	2%
> 0.5	99%	82%	17%
> 1.0	97%	41%	56%
> 1.5	88%	8%	80%
> 2.0	65%	1%	64%

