**University of Maryland, Shock Trauma Center
Department of Orthopaedics**

**Impact of Surgery on Pain in Lateral Compression Type Pelvic Fractures:
A Prospective Trial (Pelvis RCT)**

NCT02605766

University of Maryland IRB Number: HP-00060038

Principal Investigator: [name]

Safety Monitor: [name]

Version 4

June 1, 2016

TABLE OF CONTENTS

Protocol Summary	3
Key Roles.....	4
Background Information.....	4
Rationale	5
Potential Risks	5
Potential Benefits	6
Primary Outcome	6
Secondary Outcomes	6
Exploratory Outcomes	6
Description of the Study Design	6
Primary Endpoint	7
Secondary Endpoints	8
Study Population	10
Adjudicating Eligibility	11
Co-Enrollment Guidelines	11
Recruitment.....	11
Study Treatments	11
Clinical Evaluation.....	12
Participant Interviews	13
Study Schedule.....	13
Assessment of Safety	15
Data Analysis	16
Randomization	17
Data Management.....	17
Missing Data	18
Research Ethics Approval.....	18
Informed Consent.....	19
Vulnerable Populations.....	20
Participant Confidentiality	20
Study Discontinuation.....	21
Reports	21
Study Records Retention.....	21
Supporting Literature	21
APPENDIX A	23
APPENDIX B	23
APPENDIX C	See Attachements
APPENDIX D	See Attachements

PROTOCOL SUMMARY

Title	Impact of surgery on pain in lateral compression type pelvic fractures: a prospective trial
Short Title	Pelvis RCT
Type of Study	Prospective randomized control trial OR observational outcomes study
Primary Objective	To determine if surgical stabilization of lateral compression type pelvic fractures decreases patient reported pain at 2 weeks post injury compared to non-operative management.
Secondary Objective	To explore associations between treatment and: 
 1. Patient reported pain up to 1 year post injury 2. Hospital length of stay 3. Time to first mobilization (bed to chair) 4. Narcotic use up to 1 year post injury 5. Work productivity & activity impairment up to 1 year post injury 6. Health related quality of life up to 1 year post injury 7. Pelvic specific functional outcome up to 1 year post injury 8. General function up to 1 year post injury
Sample Size	We will recruit a sample size of 130 patients (65 per arm) with a minimum of 2 week follow-up for the primary outcome
Diagnosis and Main Inclusion Criteria	Lateral compression type pelvic fracture amendable to both operative or non-operative treatment per surgeon opinion in patients between the ages of 18 and 80 years of age, inclusive.
Length of Follow-up	1 year

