Study duration: We will recruit for a year and a half. Patients will be followed for 1 year. We estimate 4 years total.

Primary outcome measure: *Pain* as measured by using the arithmetic mean of the four pain severity items on the patient-reported Brief Pain Inventory assessment (BPI) 2-weeks following the patient's injury.

Secondary outcome measures: *Length of stay* will be determined by recording the admission date versus discharge date for the patient's index hospitalization. *Time to first mobilization (bed to chair)* will be determined using the physical therapy notes during the patient's index hospitalization and is defined as days post-injury and days post-operative treatment (if applicable) to time of first mobilization (bed to chair). *Narcotic use* will be determined by cross-referencing the patient's medical record during the index hospitalization and follow-up clinic appointments with patient-reported usage. *Work productivity and impairment* will be determined using the modified WPAI:SHP questionnaire. *Health related quality of life* will be measured using the VR-12 questionnaire. *Pelvic function* will be measured using the Majeed Pelvic Score.

Statistical analysis: We are interested in estimating the causal effect of operative treatment versus non-operative treatment in lateral compression type pelvic fracture patients. For all our

analyses, we will report estimates of the causal effects, standard errors, and confidence intervals. We will also report the results of tests of null hypothesis of no causal effect.

KEY ROLES

Safety Monitor- [name] will be responsible for overseeing patient safety for the study. [name] will review the enrollment numbers and medical compliance annually for the duration of the study.

Coordinating Center Principle & Sub-Investigators- [name] [name] (PI) and the sub-investigators will be responsible for developing a detailed study protocol, providing oversight on study progress and act to correct deficiencies in the conduct of the study. The PI and sub-investigators will also draft the main publications related to the study, and assist with patient consent.

Site Principle & Sub-Investigators- The site PI and sub-investigators will be responsible for oversight on local study progress. The site PI and sub-investigators will also contribute to the main publications related to the study, and assist with patient consent.

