PRIMARY OBJECTIVE

To compare 2-week post-injury assessments of patient reported pain of participants undergoing operative versus non-operative treatment following a lateral compression type pelvic fracture. We hypothesize that there will be a decrease in the Visual Analog Scale (VAS) pain scores in the operative group as compared to the non-operative group both during their hospital stay and in the short-term outpatient follow up.

SECONDARY OBJECTIVES

To compare assessments of narcotic use up to 1 year post injury of participants undergoing operative versus non-operative treatment following a lateral compression type pelvic fracture. We hypothesize that there will be a decrease in the narcotic requirements in the operative group as compared to the non-operative group throughout the 1 year follow up.

To compare assessments of time to first mobilization (bed to chair) with physical therapy of participants undergoing operative versus non-operative treatment following a lateral compression type pelvic fracture. We hypothesize that the operative group will mobilize out of bed to chair with physical therapy faster than the non-operative group.

EXPLORATORY OBJECTIVES

To explore associations between treatment and:

1. Hospital length of stay (index hospitalization)
2. Work productivity and activity impairment up to 1 year post injury
3. Health related quality of life up to 1 year post injury
4. Pelvic specific functional outcome up to 1 year post injury.

DESCRIPTION OF THE STUDY DESIGN

The Pelvis RCT study is a prospective randomized treatment trial to evaluate outcomes among operative versus non-operative lateral compression type fractures. If the patient does not agree to randomization, the patient will be asked to participate in the observational arm of the study. A schematic representation of participant enrollment can be found in the figure below.

A total of 130 patients will be enrolled (65 per arm). University of Maryland, Shock Trauma Center will act as the coordinating center for this study and all patient will be recruited from

University of Maryland, Shock Trauma Center and Indiana University Health Methodist Hospital.

Patients and/or the patient's legally authorized representative (LAR) will be approached for informed consent as soon as is feasible following determination of eligibility.

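### The primary pain outcome moves from BPI severity at 2 weeks (protocol) to a 12-week average (SAP), with no date or reason given and no 2-week comparison in the SAP text

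*SAP*

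**What the plan says.** **Protocol (Version 4, June 2016).** The Protocol Summary asks whether surgery "decreases patient reported pain at 2 weeks post injury compared to non-operative management". It defines the primary outcome measure as the "arithmetic mean of the four pain severity items on the patient-reported Brief Pain Inventory assessment (BPI) 2-weeks following the" injury, and its sample-size row asks for 130 patients "with a minimum of 2 week follow-up for the primary outcome". Pain up to 1 year is listed as a secondary objective. The Primary Objective section begins: "To compare 2-week post-injury assessments of patient reported pain of participants undergoing operative versus non-operative treatment". The Data Analysis section powers the trial for "a decrease in the primary outcome measure from 5.7 in the control group to 4.56 in the experimental group", with SD 2.3, 80% power and a 5% level.

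Other protocol wording is looser. The hypothesis in the Primary Objective section reads "We hypothesize that there will be a decrease in the Visual Analog Scale (VAS) pain scores in the operative group" and covers the hospital stay and short-term outpatient follow-up. The Primary Endpoint section names BPI pain severity without a time point. The Data Analysis section says "Primary data analysis will involve direct comparison of the change in value of the reported pain scores at the time points listed below", but no list follows.

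**SAP (December 2020), Statistical Analysis.** The primary pain analysis estimates an average treatment effect "based on a longitudinal assessment within the initial 12-weeks after the fracture". It uses a Bayesian hierarchical model with a random intercept per patient and an autoregressive correlation structure. In the SAP text, 2 weeks appears only as a visit at which 16% of outcome data were missing. The SAP is written in the past tense and includes results.

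**The concern.** The SAP describes what the longitudinal method does. It does not mention that the protocol's endpoint was at 2 weeks, and it gives no date or reason for leaving it. Among the supplied documents, the 12-week average first appears alongside results, so a reader cannot tell whether the primary result is the pre-specified one. The documents do not show whether the decision came before or after the data were seen, and nothing here asserts either.

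The 12-week average also answers a different question. It cannot be read back to the 2-week effect, because quite different 2-week effects can give nearly the same average. The stated 80% power was not calculated for the average. The SAP's subgroup and sensitivity analyses recompute average effects by displacement, fixation type or cohort. The text specifies no treatment-by-visit term from which a 2-week effect could be read.

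**Working it through.** **1. Reproduce the protocol's sample size.** Inputs from Data Analysis: means 5.7 and 4.56, SD 2.3, 5% level, 80% power, 65 per arm.

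- Difference = 5.7 − 4.56 = 1.14, which is 20% of 5.7. Standardized difference = 1.14/2.3 = 0.496.
- Two-sided two-sample t-test: 64.9 per arm for 80% power. Power is 80.1% at 65 per arm and 79.5% at 64.
- One-sided: about 51 per arm, which does not match.

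The stated 65 is therefore the two-sided answer for one score per patient. It uses one SD and no within-patient correlation, so it was not calculated for a repeated-measures average.

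**2. Weight of the 2-week score in the average (illustration).** Assumptions, none of them from the documents unless stated:

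- visits at 2, 6 and 12 weeks, treated as equally spaced;
- SD 2.3 at every visit (the protocol's value);
- 65 per arm, no missing data, a single treatment coefficient;
- random intercept plus AR(1) (the SAP's structure), with residual correlation ρ of 0.3 to 0.7 and a share *v* of 0 to 50% of the variance in the random intercept.

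Generalized least-squares weights are proportional to R⁻¹1, that is to 1, 1−ρ, 1. The random intercept does not change them. The 2-week weight is 1/(3−ρ): 0.370, 0.400 and 0.435 for ρ = 0.3, 0.5 and 0.7.

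If the 96-hour BPI in Appendix B of the protocol were also averaged, the weights would be 1, 1−ρ, 1−ρ, 1. The 2-week weight would then be (1−ρ)/(4−2ρ): 0.206, 0.167 and 0.115.

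**3. Power for the three-visit average, 65 per arm.** SD of the weighted average = 2.3 × √[*v* + (1−*v*)(1+ρ)/(3−ρ)].

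- *v* = 0, ρ = 0.3: 2.3 × √(1.3/2.7) = 1.60.
- *v* = 0.5, ρ = 0.7: 2.3 × √(0.5 + 0.5 × 1.7/2.3) = 2.15.

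| Effect at 2 / 6 / 12 weeks | Average effect | Power, SD 1.60 | Power, SD 2.15 |
|---|---|---|---|
| 1.14 / 1.14 / 1.14 | 1.14 | 98.1% | 85.3% |
| 0 / 1.71 / 1.71 | 1.08 (ρ = 0.3) to 0.97 (ρ = 0.7) | 96.8% | 72.2% |
| 1.14 / 0.57 / 0 | 0.57 | 52.4% | 32.4% |

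For row 2 the average is 1.71 × (1 − 2-week weight): 1.71 × 0.630 = 1.08 and 1.71 × 0.565 = 0.97. On the same no-missing-data basis, the 2-week comparison has 80.1% power for a difference of 1.14 at that visit.

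As a check, equal weights and compound symmetry with correlation 0.3 to 0.7 give 97.0% to 88.0% for a constant 1.14, and 48.4% to 34.8% for an average of 0.57. The pattern is the same.

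**4. Precision of a 2-week contrast.** SD 2.3, difference 1.14, two-sided t-test. The number randomized is not given in the documents, so the rows below are assumptions.

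| Per arm | Basis | Power | 95% half-width |
|---|---|---|---|
| 65 | all 130 randomized, none missing | 80.1% | 0.80 |
| 54.6 | 65 × 0.84 (16% missing) | 72.8% | 0.87 |
| 32.5 | half of 130 randomized, none missing | 50.3% | 1.14 |
| 27.3 | 32.5 × 0.84 | 43.6% | 1.25 |

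A longitudinal model or imputation may recover part of the loss. With 65 per arm, later visits taken as complete and correlation *r* with them, the variance factor is *r*² + (1−*r*²)/0.84. Power is then 73.4%, 74.6% and 76.3% for *r* = 0.3, 0.5 and 0.7.

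**The case against.** **The protocol is itself unsettled.** One section gives no time point, the hypothesis spans the hospital stay and short-term follow-up, and the Data Analysis section speaks of several time points. A multi-visit primary analysis therefore has some footing. This is true, but no protocol text sets a 12-week window or an average. The Protocol Summary and the Primary Objective section state 2 weeks explicitly, and later pain is ranked as secondary. The looseness adds to the need for a dated statement.

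**The SAP's model description is incomplete.** It names neither a treatment nor a visit main effect, so the absence of a treatment-by-visit term is weak evidence about what was fitted. That stands. The point rests on the missing 2-week contrast, not on the missing term.

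**The illustration is stylized.** The effect paths are invented. It leaves out the prior, the narcotic covariate, imputation and cohort pooling, and power is not how a Bayesian analysis is summarized. If AR(1) runs on actual time, with correlation 0.3 to 0.7 per 4 weeks, the three-visit 2-week weight is 34% to 41%. The SAP reports missingness at 2, 6 and 12 weeks only, which makes the four-visit case less likely. All of this stands. The figures show that the two targets can diverge. They do not measure an error in this trial.

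**The explanation may exist elsewhere.** A later protocol version, the figures or the main article could give the reason or visit-level results. This also stands. If so, the dated statement becomes a cross-reference.

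**Conclusion.** The concern holds and must be fixed. The mismatch is plain in the text: BPI severity at 2 weeks in the protocol, a 12-week average in the SAP, and no date, reason or 2-week contrast in the supplied text. Confidence in that is high. It does not extend to material that was not supplied.

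The size can only be illustrated. Under the assumptions above, the 2-week score carries roughly two-fifths of the weight in a three-visit average. The average can have up to 97% power when the 2-week effect is zero, or as little as 32% when the 2-week effect equals the design value but fades. The average may therefore be easier or harder to show than the 2-week difference, and it cannot stand in for it.

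**What to change.** 1. Report the between-arm difference in mean BPI severity at 2 weeks, by assigned arm in the randomized cohort, as the protocol-aligned primary result. Give the estimate, its 95% interval and the null-hypothesis test promised under Statistical analysis in the Protocol Summary.
2. The estimate may come from the existing longitudinal model with treatment-by-visit terms added. Describe that model, the restriction to randomized patients and any covariate adjustment as analysis choices, not as protocol-specified. Do not condition this estimate on narcotic use measured after treatment, which treatment may itself affect.
3. Keep the 12-week average and its posterior probabilities. Label them as a changed or additional estimand, give the date and reason for the change, and state which visits are averaged.
4. In the same dated statement, reconcile the protocol's VAS, change-in-value and time-point wording with the BPI definition at 2 weeks.

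The cost is one more analysis of data already held, plus the statement. Nothing is discarded. The drawback is lower precision in the randomized cohort: about 73% power if 65 per arm were randomized with 16% missing, or about 44% if only half of the 130 were randomized with the same missingness (complete cases in both).
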